12. STUDY ASSESSMENTS

After informed consent is obtained, a short targeted medical and ocular history will be taken, which focuses on whether there is any known corneal pathology, or other ocular or systemic condition which would affect the study assessments needed.

Then the following assessments will take place:

1. CCT measurement using Occuity device
2. CCT measurement using Pentacam device
3. CCT measurement using Lenstar device
4. Instillation of Minims Proxymetacaine Hydrochloride 0.5% eye drops to the study eye
5. CCT measurement using Ultrasound Pachymeter

13. DISCONTINUATION/WITHDRAWAL OF PARTICIPANTS FROM STUDY TREATMENT

A participant has the right to withdraw from the study at any time and for any reason and is not obliged to give his or her reasons for doing so. The participant may withdraw/be withdrawn from further study procedures at any time in the interests of the participant's health and well-being, or for any of the following reasons:

- Significant protocol deviation.
- Participant non-compliance, intentional or non-intentional, with study requirements.
- An adverse event (SAE, ADE), which requires discontinuation of the study involvement or results in inability to continue to comply with study procedures.
- Any other reason that may compromise the safety of the participant or the integrity of study data in the opinion of the investigator.

The reason for withdrawal from during the study visit will be recorded. For all SAEs/ADEs, appropriate follow-up visits or medical care will be arranged, with the agreement of the participant, until the AE has resolved, stabilised or a non-study related causality has been assigned. Any data collected prior to withdrawal will be included in the final analysis unless consent for this is withdrawn.

14. DEFINITION OF END OF STUDY

The end of study is the date of the last assessment of the last participant.

15. INTERVENTIONS

15.1 Description of Study device

The Occuity PM1 device utilises both LED lights and low intensity infrared radiation. There are a total of 9 LED lights in a partial ring, the lights are at a radius of 8.75mm and spaced at 30° intervals. The total power is 2.4 mWm⁻² which is within the 10 mWm⁻² blue light hazard eye safety limit.

The infrared radiation is at a wavelength of 1310nm, and the maximum power is 50µW. The expected exposure to this radiation is less than 10 seconds in total, which makes it significantly under both the 2.5mW eye safe limit for 10 second exposure and the 158µW eye safe limit for 2-hour exposure, therefore the device is Class 1 eye safe according to BS EN 60825.

To take the measurement, the device will first be held above the study eye to achieve good alignment, after which the start button can be pressed to begin the measurement process. Once completed, the measurement will be displayed on the digital touchscreen of the device.

15.2 Adherence to Study Treatment

N/A

15.3 Accountability of the Study Treatment

N/A

15.4 Concomitant Medication / Therapies

N/A

ASSESSMENT OF SAFETY

15.5 Definitions

A serious adverse event is any untoward medical occurrence that:

- Results in death,
- Is life-threatening,
- Significant decline in vision (Defined as irreversible loss of 10 EDTR letters)
- Requires inpatient hospitalisation or prolongation of existing hospitalisation,
- Results in persistent or significant disability/incapacity, or
- Is a congenital anomaly/birth defect.
- Other important medical events*

*Other events that may not result in death, are not life threatening, or do not require hospitalisation, may be considered a serious adverse event when, based upon appropriate medical judgement, the event may jeopardise the participant and may require medical or surgical intervention to prevent one of the outcomes listed above.

15.6 Reporting Procedures for Serious Adverse Events

A serious adverse event (SAE) occurring to a participant will be reported to the REC if Chief Investigator deems the event results from, and is an unexpected effect of, administration of any of the research procedures. Reports of related and unexpected SAEs should be submitted within 15 days of the Chief Investigator becoming aware of the event, using the NRES report of serious adverse event form (see NRES website).

15.7 Recording and Reporting Procedures for All Adverse Events

In the event of an adverse event occurring in this study, an adverse event report form will be completed. If the adverse event has potential to cause harm to the participant, the sponsor will be informed.

16. DATA HANDLING AND RECORD KEEPING

All participants will be assigned a study specific participant number. Study data will be initially recorded on a paper case report form (CRF), which will be kept securely in the ophthalmology research office in a locked cabinet. The anonymised data will then be entered into an electronic database (Identified only by participant number), which is operated on a secure system run by the trust. The electronic database will be password protected only be accessible by authorized members of the study team. The name and any other identifying detail will NOT be included in any study data electronic file.

17. DATA ANALYSIS

17.1 Description of Analysis Populations

All participants who satisfy the eligibility criteria and are subsequently enrolled and complete the study procedures will be included in the data analysis.

17.2 Analysis of Endpoints

On completion of data collection, the primary endpoint will be analysed using paired tests or non-parametric equivalents, to compare the CCT measurement achieved using the ultrasound pachymeter and the Occuity PM1 device, and then between the values obtained from the Lenstar, Pentacam and Occuity PM1 device. The level of statistical significance will be set at $p < 0.05$.

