2. SYNOPSIS

Study Title	Assessment of the Occuity PM1 pachymeter
Research question / hypothesis	Is the Occuity pachymeter non inferior in it's measurement of central corneal thickness compared to the ultrasound pachymeter, Lenstar and Pentacam.
Study Design	Research Study
Study Participants	Volunteers with no corneal pathology
Planned Sample Size	82-100 participants
Follow-up duration	N/A
Planned Study Period	1 month
Primary Objective	To determine whether the Occuity PM1 device is non-inferior in measuring central corneal thickness when compared to ultrasound pachymetry, the Lenstar and the Pentacam.
Secondary Objectives	The Investigation aims to assess long-term safety of the Occuity PM1 device when used under the conditions and for the purposes intended, to ensure it will not compromise the clinical condition or the safety of patients, or the safety and health of users or, where applicable, other persons.
Primary Endpoint	The central corneal thickness measurements taken by the three devices: Occuity PM1, the ultrasound pachymeter and Lenstar. Demonstrating that the Occuity PM1 Pachymeter is not inferior to the LenStar in terms of equivalency to a 95% confidence level using the Bland Altmen equation/approach based on +/-20micron equivalency.
Secondary Endpoints	If evidence is not sufficient to demonstrate that the PM1 Pachymeter does not perform outside of the target range, it is understood that further investigation may be required. If it is deemed that further clinical investigation(s) are required, it is understood that a new MHRA application will be undertaken.
Safety Outcomes	The type and number of adverse events, serious adverse events and any other device issues will be recorded. Adverse events and devices issues not reflected on the product label will be reported to the manufacturer and, for the Occuity product, will be dispositioned according to the Sponsor's complaint handling procedures for post-market products.
Intervention (s)	N/A

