The device has an intuitive touchscreen display interface, and a series of 9 LEDs which provides the illumination needed to align the device in front of the eye. Once alignment is achieved, the measurement can take place by pressing the start button on the touchscreen display. During preliminary testing at the parent company, it has been shown the alignment and measurement process takes less than 10 seconds in total, after which a reading will be shown on the digital display of the device. The device is reported to have high reliability (variation of approximately 10um with repeat readings of the same eye), and comparable results to the Lenstar LS900 Biometer during initial testing.

The LED light system consist of a partial ring of 9 white LEDs at a radius of 8.75mm and spaced at 30° intervals. The total power is 2.4 mWm⁻² which is will within the 10 mWm⁻² blue light hazard eye safety limit. The maximum power of the infrared beam is 50µW, which given the expected exposure time of less than 10 seconds, is considered Class 1 eye safe according to BS EN 60825.

Lenstar LS 900 (Haag-Streit AG, Koeniz, Switzerland)

The Lenstar is an optical device which utilises an 820nm super-luminescent diode and allows for high resolution measurements of the structures in the eye, including CCT. Its use is well established in the hospital clinic setting, and measurements do not require the use of anaesthetic drops or corneal touch. A drawback of this device is that it is large and heavy, and therefore not portable or as fast to use, unlike the ultrasound pachymeter or the Occuity PM1 device.

Pentacam (Oculus Optikgerate GmbH (Germany)

Very similar to the Lenstar, the Pentacam is an optical device which also utilises an 820nm super-luminescent diode and allows for high resolution measurements of the structures in the eye, including CCT. Its use is well established in the hospital clinic setting, and measurements do not require the use of anaesthetic drops or corneal touch. A drawback of

this device is that it is large and heavy, and therefore not portable or as fast to use, unlike the ultrasound pachymeter or the Occuity PM1 device.

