4. AIMS AND OBJECTIVES

Primary Objective

To determine whether the Occuity PM1 device is non-inferior in measuring central corneal thickness when compared to ultrasound pachymetry, the Lenstar and the Pentacam.

Secondary Objective

The Investigation aims to assess long-term safety of the Occuity PM1 device when used under the conditions and for the purposes intended, to ensure it will not compromise the clinical condition or the safety of patients, or the safety and health of users or, where applicable, other persons.

If the evidence collected during this investigation is not sufficient to demonstrate that the PM1 Pachymeter does not perform under the conditions and for the purposes intended, it may be deemed possible that further investigation may be required. If it is deemed that further clinical investigation(s) are required, it is understood that a new MHRA application will be undertaken.

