6.2 Primary and Secondary Endpoints/Outcome Measures

The central corneal thickness measurements taken by the three devices: Occuity PM1, the ultrasound pachymeter and Lenstar. Demonstrating that the Occuity PM1 Pachymeter is not inferior to the LenStar in terms of equivalency to a 95% confidence level using the Bland Altmen equation/approach based on +/-20micron equivalency.

Occuity outlines the target range of the PM1 to be within 300-800um. This is because we have already tested this target range with known artefacts. However, the patient population which

is being evaluated will consist only of patients with no known corneal abnormalities, corrective refractive surgeries, ocular inflammatory conditions etc.

It is likely that ~95% of corneal thicknesses which are measured will be within the range of 480um to 620um, therefore ~5% will be outside of the expected range. However, despite there being no history of the pre-stated conditions, there is still the likelihood of this study being able to assess patients with thick/thin corneas as part of the scope, as this is the percentage population who naturally have very thin or very thick corneas.

Secondary Endpoint

If evidence is not sufficient to demonstrate that the PM1 Pachymeter does not perform outside of the target range, it is understood that further investigation may be required. If it is deemed that further clinical investigation(s) are required, it is understood that a new MHRA application will be undertaken.

SAFETY OUTCOMES MEASURES

The type and number of adverse events, serious adverse events and any other device issues will be recorded. Adverse events and devices issues not reflected on the product label will be reported to the manufacturer and, for the Occuity product, will be dispositioned according to the Sponsor's complaint handling procedures for post-market products.

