7. SAMPLING

To achieve a statistically significant result in this crossover, non-inferiority study, with the alpha error set at <0.025, and power at 0.95, and a non-inferiority limit of 2 μ m, 163 eyes will be required, which would likely mean 82 to 100 participants, assuming most are able and willing to have tests performed on both eyes. Calculations are based on the formula:

$n = f(\alpha, \beta) \times 2 \times \sigma^2 / d^2$ (where σ is the standard deviation).

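### The primary analysis in section 17.2 (paired tests at p < 0.05, no margin) does not carry out the ±20 micron Bland-Altman criterion against the Lenstar that the protocol sets for the primary endpoint

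*Protocol*

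**What the plan says.** The criterion stands in the same words in the protocol's synopsis and in section 6.2. The comparator is the Lenstar and the confidence level is 95%: "Demonstrating that the Occuity PM1 Pachymeter is not inferior to the LenStar in terms of equivalency to a 95% confidence level". The method is Bland-Altman and the margin is ±20 microns, as the rest of that sentence shows: "using the Bland Altmen equation/approach based on +/-20micron equivalency".

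Section 17.2, the only part of the data analysis section that treats this endpoint, says that "the primary endpoint will be analysed using paired tests or non-parametric equivalents". It compares ultrasound with the PM1 first, "and then between the values obtained from the Lenstar, Pentacam and Occuity PM1 device", and sets significance at p < 0.05. It mentions no margin, confidence interval, limits of agreement, or equivalence or non-inferiority hypothesis.

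Two other places bear on the point. The primary objective in section 4 is for the PM1 to be "non-inferior in measuring central corneal thickness when compared to ultrasound pachymetry, the Lenstar and the Pentacam". Section 7 (Sampling) sizes the study at 163 eyes for a limit of 2 microns, "assuming most are able and willing to have tests performed on both eyes", and gives no value for the SD.

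**The concern.** A paired test without a margin asks whether the mean difference is exactly zero. The protocol's criterion asks whether the difference stays within ±20 microns. Non-significance does not show agreement, and significance does not show a difference that matters.

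This is the sole primary analysis of a device-agreement study. As written, a non-significant p-value could be reported as non-inferiority, or a trivial offset could count against an acceptable device. Two rules for one endpoint also leave room to choose between them after the data are seen.

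The criterion itself is not fully defined. Section 6.2 does not say which quantity must lie within ±20: (a) the 95% confidence interval of the mean difference, (b) the 95% limits of agreement, or (c) the outer confidence bounds of those limits.

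**Working it through.** **The plan's own figure.** Section 7 uses n = f(α, β) × 2 × σ² / d², with α = 0.025, power 0.95 and d = 2. Read as one-sided, f = (1.960 + 1.645)² = 12.99. Setting 12.99 × 2 × σ² / 4 = 163 gives σ = 5.01; σ = 5 gives 162.4, rounded up to 163. The stated size is thus consistent with an SD of 5, which the protocol does not state. With the factor 2 in the formula, this is a per-device SD. The SD of differences would be 5 × √2 = 7.07 if the two devices' errors are independent.

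**Assumed SDs of differences (microns).** Section 3 reports "variation of approximately 10um with repeat readings of the same eye" without defining variation.
- Taken as an SD: 10 if the Lenstar is error-free, or 10 × √2 = 14.1 with equal Lenstar error.
- Taken as a 95% repeatability limit: 10 / (1.96 × √2) = 3.6, or 5.1 with equal Lenstar error.
- From section 7: 5 if taken directly as the SD of differences, 7.07 if per device.
- SD 9 and SD 15 are illustrations only.

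Two values of n are used: 163 eyes treated as independent, and 82 units as a cautious allowance for two eyes per participant.

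**Smallest observed mean difference that is significant**, t(0.975, n−1) × SD / √n, with t = 1.975 (n = 163) and 1.990 (n = 82):

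| SD | n = 163 | n = 82 |
|---|---|---|
| 3.6 | 0.6 | 0.8 |
| 5 | 0.8 | 1.1 |
| 7.07 | 1.1 | 1.6 |
| 10 | 1.5 | 2.2 |
| 14.1 | 2.2 | 3.1 |

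All are far inside ±20.

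**The test against the criterion.** Simulation with normal differences and independent units. With m the observed mean difference and s the observed SD, the rules are:
- (a) |m| + t·s/√n < 20
- (b) |m| + 1.96·s < 20
- (c) |m| + 1.96·s + t·s·√(1/n + 1.96²/(2(n−1))) < 20

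Cells show n = 163 / n = 82.

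| Bias, SD | Test significant | (a) met | (b) met | (c) met |
|---|---|---|---|---|
| 3, 5 | >99% / >99% | 100% / 100% | >99% / >99% | >99% / >99% |
| 2, 7.07 | 95% / 71% | 100% / 100% | >99% / >99% | 99% / 84% |
| 3, 7.07 | >99% / 97% | 100% / 100% | >99% / 99% | 89% / 64% |
| 0, 7.07 | 5% / 5% | 100% / 100% | 100% / 100% | >99% / 98% |
| 0, 10 | 5% / 5% | 100% / 100% | 44% / 41% | 1% / 1% |
| 0, 15 | 5% / 5% | 100% / 100% | 0% / 0% | 0% / 0% |

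At zero bias the true limits are ±1.96 × 10 = ±19.6 and ±1.96 × 15 = ±29.4. The test is non-significant 95% of the time in both cases, because it does not respond to spread. A Wilcoxon signed-rank test with 82 units behaves the same way: significant 99.95% of the time at bias 3, SD 5, and non-significant 95% of the time at bias 0, SD 15.

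**The case against.** The strongest reply is that the criterion is in the protocol, that section 17.2 may only add tests to it, and that an analysis plan not shown here may implement Bland-Altman. Paired tests can also be run against a margin as two one-sided tests. But section 17.2 is not silent: it says how the primary endpoint will be analysed and does not refer to ±20. An analysis plan that followed one passage would depart from the other. A shifted null is possible but nowhere stated, and even then a test of the mean would not deliver limits of agreement.

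Some of the reply stands:
- The SD of 5 implied by section 7 is per device. At 7.07 and bias 3, rule (c) is met only 89% / 64% of the time, so that example is not equally clear on the strictest reading. The conflict remains on (a) and (b), and on (c) with 163 eyes at bias 2.
- The failure to detect spread needs an SD of about 10 or more, which the protocol does not establish. It is absent at 7.07 and never arises under (a).
- The 95% non-significance at zero bias is simply the test's 5% error rate.
- The order in which section 17.2 lists the comparisons is a minor matter and not a declared hierarchy. The choice among (a), (b) and (c) is detail that an analysis plan could settle; the contradiction does not depend on it.

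**Conclusion.** The concern holds and should be corrected before data collection. The protocol sets one criterion for its primary endpoint and prescribes a different analysis for it.

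That a trivial difference can be significant while ±20 is met is true on every reading of the criterion. That the test misses excessive spread is true only under (b) or (c), and only if the SD of differences is near or above 10 microns. All sizes assume an SD, normal differences and independent units. The contradiction between the sections needs none of these assumptions.

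**What to change.** Replace the primary analysis in section 17.2 with a Bland-Altman analysis of PM1 minus Lenstar: mean difference and 95% limits of agreement, each with 95% confidence intervals, allowing for two eyes per participant, judged against ±20 microns.

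Also state, before data collection:
- which quantity, (a), (b) or (c), must lie within ±20. The protocol does not settle this and the choice is the sponsor's. Rule (a) does not limit the spread of individual differences; (c) is the strictest.
- whether ultrasound and Pentacam, reported the same way, are supportive (section 6.2 ties the criterion to the Lenstar) or must also pass (section 4 joins all three).
- that paired-test p-values are descriptive.
- whether the 2 micron limit in section 7 serves a separate question about the mean difference.

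The cost is protocol wording and modest programming on the same measurements. The fix itself adds no enrolment, but 163 eyes were sized for 2 microns, so precision for the chosen rule must be restated. At zero bias the largest observed SD of differences that fits is as follows (n = 163 / 82):
- (a) 20·√n/t = 129 / 91, so effectively always met
- (b) 20/1.96 = 10.2 / 10.2
- (c) 20/[1.96 + t·√(1/n + 1.96²/(2(n−1)))] = 9.0 / 8.6

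At a true SD of 9 the chance of meeting the rule is (a) 100% / 100%, (b) 95% / 86%, (c) 32% / 16%. The sponsor should see these figures before choosing.

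### Section 17.2 analyses the primary endpoint by a paired location test or its rank equivalent; neither applies the ±20 µm Bland-Altman criterion, and the two can disagree on the same data

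*Protocol*

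**What the plan says.** Protocol Section 17.2 (Analysis of Endpoints) states that "the primary endpoint will be analysed using paired tests or non-parametric equivalents". These compare PM1 with the ultrasound pachymeter, and then with the Lenstar and Pentacam. "The level of statistical significance will be set at" p<0.05; whether this is one-sided or two-sided is not said. The section mentions no margin, interval or limits of agreement.

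Section 6.2 (and the Synopsis) sets success on the same endpoint, PM1 against the Lenstar, at 95% confidence, "using the Bland Altmen equation/approach based on +/-20micron equivalency".

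Section 7 (Sampling) sizes the study "with the alpha error set at <0.025, and power at 0.95", and with "a non-inferiority limit of 2 μ m, 163 eyes will be required". Its formula is n = f(α,β) × 2σ²/d², "where σ is the standard deviation"; no value of σ is given.

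On how readings are taken, Section 15.1 says that "the device will first be held above the study eye to achieve good alignment". Section 3 reports a "variation of approximately 10um with repeat readings of the same eye".

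**The concern.** An agreement study has two questions to answer: how large is the average bias, and how far can a single reading be wrong? Section 7 is built on the first, as a limit on a mean difference. The Bland-Altman criterion in Section 6.2 covers both, because limits of agreement combine the mean with the spread.

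A signed-rank test, the usual non-parametric equivalent of a paired t-test, answers neither. It concerns the pseudo-median and caps the weight of any one large difference. The paired t-test at least concerns the mean, but it too tests only location. Section 17.2 therefore permits two analyses with different targets, and neither applies the endpoint's own criterion.

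PM1 is hand-held and has to be aligned, so an occasional gross misreading is conceivable. In that situation the two tests part company, and the reported conclusion can depend on which one is used.

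**Working it through.** **1. The plan's own figure.** Taking alpha as one-sided 0.025 with power 0.95, f = (1.960 + 1.645)² = 12.995. Because σ is not stated, 163 cannot be reproduced from the stated inputs alone. Solving backwards with d = 2 gives σ = √(163 × 4 / (2 × 12.995)) = 5.01. With σ = 5, n = 12.995 × 2 × 25/4 = 162.4, rounded up to 163. This is a formula for a difference in means. If σ is the SD of one device's readings around the true value and errors are independent between devices, the SD of the differences is √2 × 5 = 7.07 µm.

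**2. Assumptions for the comparison.** n = 163 independent eyes, core SD 7.07 µm, and 8 eyes (8/163 = 4.9%) grossly misread. The SD is back-solved. The number, size and direction of the errors are not in the Protocol. Tests are at two-sided 0.05.

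**3. What theory predicts.**
- *Zero bias, 8 errors of +50 µm.* The mean difference is 8 × 50/163 = 2.45 µm. The SD is √(50 + 0.0491 × 0.9509 × 2500) = 12.9 and the standard error 12.9/√163 = 1.01, so t is about 2.4. The limits of agreement are 2.45 ± 1.96 × 12.9, or about −22.9 to +27.8 µm. The rank-based (Hodges-Lehmann) estimate averages only 0.6 µm in simulation.
- *Bias +2 µm, four errors of +50 and four of −50 µm.* The mean stays at 2 µm. The SD is √(50 + 0.0491 × 2500) = 13.1 and the standard error 1.03, so t is about 1.94, close to the critical value. Without the errors, t would be 2/(7.07/√163) = 3.6. The limits are 2 ± 25.8, or about −23.8 to +27.8 µm.
- *Bias −2 µm, 8 errors of +50 µm.* The mean is −2 + 2.45 = 0.45 µm, so the errors cancel the bias and the t-test sees almost nothing.

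**4. Simulation: share of studies with p<0.05.**

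| True bias (µm) | 8 eyes misread by (µm) | Paired t-test | Signed-rank |
|---|---|---|---|
| 0 | no errors | 5% | 5% |
| 0 | +50 | 78% | 16% |
| 0 | +30 | about 50% | about 18% |
| +2 | ±50 | 50% | 91% |
| +2 | ±30 | 82% | 91% |
| −2 | +50 | 0.4% | 54% |
| −2 | +30 | 4% | 54% |

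With zero bias and 8 errors of +50 µm, the t-test was significant and the signed-rank test was not in 62% of studies. Raising the core SD to 10 µm gives 62% against 16% for that scenario, so the gap does not hang on 7.07.

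**5. Do the location tests expose gross errors at all?** Not reliably. With core SD 5 or 10 µm, zero bias and 4, 8 or 16 errors split between +100 and −100 µm, the t-test rejected in 0% of runs and the signed-rank test in about 2–5%. With only 3 errors of +100 µm the figures were 17–18% and 6–7%.

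**6. Do the ±20 µm limits?** The point limits of agreement fell outside ±20 µm in 100% of the runs with errors of 50 or 100 µm. With 8 errors of +30 µm and zero bias they did so in about 60%. A count of eyes beyond 20 µm is therefore useful beside them.

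**The case against.** A reader might infer something stronger: that gross misreadings would trigger a switch to the rank test, which would then hide them and so favour the device. The Protocol does not support this, for three reasons.

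- **No trigger is written.** Section 17.2 names no normality check and no switching rule. In the contaminated simulations a Shapiro-Wilk test would flag non-normality essentially every time, but the Protocol nowhere says that such a test decides. A selection rule is commonly left to the SAP, which is not shown, so its absence is not the finding.
- **The direction is not general.** The rank test is the lenient one with zero bias and same-direction errors. In the last four rows of the table the t-test is the one that misses a real bias.
- **Errors need not vanish from the result.** Section 6.2 still defines success by Bland-Altman, and run against ±20 µm it would show errors of the size assumed.

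It is also fair that nothing in the Protocol establishes how often PM1 misreads grossly. Section 3 reports only about 10 µm of repeat variation. Section 17.3, which leaves inclusion of spurious data to the chief investigator, is a more direct route by which bad readings could drop out, but that is a separate matter.

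All of this stands against the stronger reading. It does not remove the mismatch: the section that says how the primary endpoint will be analysed omits the analysis that defines the endpoint, and offers two tests that estimate different things.

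**Conclusion.** The point holds in this limited form. As written, Section 17.2 does not apply the criterion of Section 6.2, and one of its two permitted tests also departs from the mean on which Section 7 is based. Where a few readings are grossly wrong, the choice of test can change the conclusion substantially, either way. Neither test is a dependable detector of such readings.

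The percentages rest on independent eyes (the plan measures both eyes of most participants), a back-solved SD, and assumed numbers, sizes and directions of error. They show what can happen, not what is expected. With no gross errors the two tests agree closely. No claim of a systematic advantage to the device should be made.

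**What to change.** In Section 17.2, delete the non-parametric alternative for the primary endpoint and state the primary analysis as:

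1. the mean PM1-minus-comparator difference with its 95% CI, bootstrapped by participant if the differences are skewed;
2. 95% limits of agreement judged against ±20 µm, using the empirical 2.5th and 97.5th percentiles if the differences are not normal;
3. the number and proportion of eyes differing by more than 20 µm in absolute value, with a CI.

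The three parts belong together: keeping the mean alone would still miss errors that cancel.

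The cost is a short change to one section and no extra data. The downside is wider intervals when outliers are present, which reflects the error actually observed.

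### Neither the paired tests, the ±20 µm limit against Lenstar nor the 2 µm sample-size limit shows whether PM1's random error exceeds that of the established devices, which the non-inferiority objective needs

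*Protocol*

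**What the plan says.** The primary objective (Synopsis and Section 4) is relative and names three comparators: "To determine whether the Occuity PM1 device is non-inferior in measuring central corneal thickness when compared to ultrasound pachymetry, the Lenstar and the Pentacam".

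The Protocol then fixes three separate yardsticks:

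- **Section 6.2 (and Synopsis), the endpoint:** "Demonstrating that the Occuity PM1 Pachymeter is not inferior to the LenStar in terms of equivalency to a 95% confidence level", judged "using the Bland Altmen equation/approach based on +/-20micron equivalency". Lenstar is the only device named in this criterion.
- **Section 7, the sample size:** "with the alpha error set at <0.025, and power at 0.95", "and a non-inferiority limit of 2" µm, leading to "163 eyes will be required, which would likely mean 82 to 100 participants". The formula is one for comparing means.
- **Section 17.2, the analysis:** paired tests or non-parametric equivalents at p<0.05, comparing PM1 with ultrasound "and then between the values obtained from the Lenstar, Pentacam and Occuity PM1 device".

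Every participant is to be measured on all four devices (Sections 6.1, 8 and 12).

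**The concern.** To say that a new device is non-inferior to those in use is to say that it measures no worse than they do. For a measuring device, that covers systematic error (bias) and random error (scatter). The paired tests in Section 17.2 and the 2 µm limit in Section 7 concern the average difference. A device with no bias but much more scatter can satisfy both.

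The Bland-Altman criterion does respond to scatter, but to the scatter of the PM1-Lenstar difference, to which both devices contribute. Meeting ±20 µm does not show that PM1 is as precise as Lenstar. Missing it does not show that PM1 is the worse of the two. How far the established devices differ among themselves would put the PM1 result in context. Those readings are planned, but no section uses them as a benchmark.

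At stake is the wording of the main conclusion. The trial could report non-inferiority for a noisier device, or count a comparator's own error against PM1.

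**Working it through.** **1. The Protocol's own figure.** Section 7 gives n = f(α, β) × 2 × σ²/d², with α = 0.025 (taken as one-sided; the Protocol does not say), power 0.95 and d = 2 µm. No value of σ is given, only "where σ is the standard deviation".

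- f = (1.960 + 1.645)² = 12.995.
- With σ = 5: n = 12.995 × 2 × 25 / 4 = 162.4, rounded up to 163.
- Neighbouring values do not fit: σ = 4.5 gives 132 and σ = 5.5 gives 197.

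So 163 eyes implies σ of about 5 µm. The Protocol does not say whether this is one device's error SD or the SD of paired differences. In the second case, with equal device errors, the per-device SD is 5/√2 = 3.54 µm.

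**2. How much PM1 error fits inside ±20 µm.** Assume independent device errors and zero bias.

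- SD of the difference: SD_diff² = SD_PM1² + SD_Lenstar².
- Point limits of agreement at ±20 µm: SD_diff = 20/1.96 = 10.20 µm.
- Largest passing ratio = √(10.20² − SD_Lenstar²) / SD_Lenstar.

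Section 6.2 asks for a 95% confidence level without saying to what it applies. If the 95% confidence bounds of the limits must also lie inside ±20 µm, with 163 eyes treated as independent, SD_diff may be at most 20 / [1.96 + 1.96 × √(1/163 + 1.96²/(2 × 162))] = 9.00 µm.

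| Assumed Lenstar error SD (µm) | Largest ratio, point limits | Largest ratio, confidence bounds (n=163) |
|---|---|---|
| 3 | 3.25 | 2.83 |
| 4 | 2.35 | 2.01 |
| 5 | 1.78 | 1.50 |
| 6 | 1.38 | 1.12 |
| 7 | 1.06 | 0.81 |
| 8 | 0.79 | 0.51 |

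The ratio is 1 at a Lenstar SD of 10.20/√2 = 7.2 µm (point limits) or 9.00/√2 = 6.4 µm (confidence bounds). Above that, ±20 µm is stricter than parity.

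**3. Sensitivity at a Lenstar SD of 5 µm.** A bias of 2 µm lowers the point-limit ratio from 1.78 to 1.54, and a bias of 5 µm lowers it to 1.16. With n = 82, as if the two eyes of a person carried one eye's information, the confidence-bound ratio is 1.39.

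**4. Chance of passing.** The simulation used 82 participants with two eyes each, Lenstar SD 5 µm, zero bias and between-eye error correlation 0 to 0.5. A PM1 with 1.5 times Lenstar's error had both point limits inside ±20 µm in 91-95% of trials. At about 1.8 times it passed in about 30%. If the confidence bounds must also fit, 1.5 is already the break-even ratio, and fewer than half of such trials pass.

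**5. What the other yardsticks would detect.** At the 1.78 ratio, the 95% confidence interval of the mean difference has half-width 1.96 × 10.20/√163 = 1.57 µm. An unbiased PM1 with that much extra error would therefore usually show no significant difference and an interval near zero. Neither a paired test nor a 2 µm limit on the mean is aimed at the extra scatter.

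**6. The missing benchmark.** Two devices with 5 µm error each would have limits of agreement of ±1.96 × 5 × √2 = ±13.9 µm. Seen beside that, PM1-Lenstar limits close to ±20 µm would be visibly wider.

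**The case against.** **The Protocol defines its own term.** Section 6.2 equates not being inferior with equivalency within ±20 µm. A pre-set absolute limit is an accepted criterion for agreement, and any margin lets a somewhat worse device through. This stands: ±20 µm is legitimate as an agreement criterion. It does not support the wider conclusion in the objective, which names three devices and is relative.

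**Detail belongs in the statistical analysis plan.** That plan is not shown, and variance-component methods are usually left to it. This stands for the methods. It does not cover the mismatch, because the Protocol itself states the objective, the criterion and the type of test.

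**Lenstar and Pentacam may already be compared.** The sentence in Section 17.2 can be read that way. Even so, a paired test compares their locations and gives no benchmark for scatter.

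**A stronger reading: a PM1 with 1.8 times Lenstar's error would pass.** The Protocol does not support this as a fact. The figure needs a Lenstar SD of 5 µm, zero bias and point limits. The 5 µm is only back-solved from a sample size with unstated σ, and nothing identifies it as Lenstar's error.

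**A second stronger reading: the claim must rest on the ratio of error SDs.** That changes the estimand, and without a margin it cannot be met reliably. With three equal devices at 5 µm, the estimated ratio spans about 0.74-1.37 (between-eye correlation 0.5). The three-device decomposition can also fail: with SDs of 2 µm for Lenstar, 10 µm for PM1 and an assumed 5 µm for Pentacam, Lenstar's estimated variance is negative in about 18-21% of trials.

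**Conclusion.** The point holds as a mismatch between a relative objective and yardsticks that cannot answer it. Paired tests and the 2 µm limit address location. The ±20 µm criterion addresses agreement with one comparator and mixes two devices' errors.

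The size can only be given as a range. The largest passing PM1/Lenstar ratio is about 3.3, 2.3, 1.8, 1.4, 1.1 and 0.8 for Lenstar SDs of 3, 4, 5, 6, 7 and 8 µm, and about 1.5 at 5 µm if confidence bounds must also fit. All of this assumes independent errors and zero bias; bias lowers every figure. A PM1 noisier than Lenstar can have limits inside ±20 µm only if Lenstar's SD is below about 7.2 µm (6.4 µm with confidence bounds).

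A reader should not infer that PM1 is noisier than Lenstar, or that ±20 µm is an invalid limit. Nothing in the Protocol shows either. This should be corrected before analysis, but it does not affect the data to be collected.

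**What to change.** 1. In Section 17.2, replace reliance on paired significance tests with bias and 95% limits of agreement for PM1 against each of the three comparators, with confidence intervals clustered by participant.
2. Beside them, report the Lenstar-Pentacam limits of agreement, and ultrasound against each, as the benchmark. Ultrasound always comes last and after anaesthetic, which Section 3 says raises the reading, so its bias should be read with that in mind.
3. Word the ±20 µm result as agreement within ±20 µm of Lenstar, not as evidence that PM1 is no worse than Lenstar. State whether the point limits or their confidence bounds must lie inside.
4. Reconcile ±20 µm in Section 6.2 with the 2 µm limit in Section 7, stating what each applies to, and state σ and its source.
5. Optionally, report device-specific error SDs (Grubbs decomposition or a mixed model with device-specific residual variances, bootstrapped by participant) as a supportive analysis. It assumes independent device errors. Repeating it with ultrasound as third device checks this only in part, since error shared by PM1 and Lenstar would remain. It should not decide the claim unless a margin for the ratio is set in advance.

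Cost: a little more analysis and a narrower stated conclusion. No further readings, visits or participants are needed.
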